2.2.4. Safety Parameters

- Incidence rate and severity of treatment-emergent adverse events (TEAEs) and SAEs
- Incidence rate and severity of study drug-related TEAEs and SAEs
- Vital signs
- Electrocardiogram (ECG)
- Clinical laboratory test results

2.3. Overall Study Design

[figure not shown]
Study Design:

This Phase 2 pilot study is comprised of multiple cohorts each for a different study population. Each cohort is an independent randomized, double-blind, placebo-controlled sub-study to investigate the efficacy, safety, tolerability, PK and immunogenicity of KPL-716 administered SC in reducing pruritus in diseases characterized by chronic pruritus. The following chronic pruritic diseases will be studied. Each cohort will be analyzed independently. Pooled cohorts may be analyzed as well.

[figure not shown]
- Cohort 1: Chronic Idiopathic Urticaria (CIU)
- Cohort 2: Chronic Idiopathic Pruritus (CIP)
- Cohort 3: Lichen Planus (LP)
- Cohort 4: Lichen Simplex Chronicus (LSC)
- Cohort 5: Plaque Psoriasis (PPs)

Each cohort will enroll up to 26 subjects and contain three periods:

- Screening Period (Day-28 to Day-1, minimum 14 days and maximum 28 days)
- Treatment Period (Day 1 [Baseline] to Week 8)
- Follow-up Period (After Week 8 to Week 18)

Figure 1: Cohort Study Design Diagram**Randomization:**

All subjects who are eligible for study participation will be randomized prior to study drug administration. Eligible subjects will be randomized to receive KPL-716 or placebo (Figure 2). The first 12 subjects of each cohort will be randomized to the KPL-716 and placebo arms in a 3:1 randomization ratio. The rest of the 14 subjects will be randomized in a 1:1 ratio. The randomization will be based on a computer-generated treatment randomization schedule prepared before the study by the Sponsor or designee.

Figure 2: Treatment Assignment Design Diagram**Efficacy assessments:**

Efficacy in reduction of pruritus will be assessed via daily recording of WI-NRS as well as on-site assessment of Pruritus VAS and 5-D Pruritus. Improvement in sleep will be assessed via daily recording of two NRS scales, one for difficulty falling asleep and the other for quality of sleep. Impact on sleep will also be assessed via on-site Sleep Loss VAS. Impact on quality of life will be assessed via on-site PROs: DLQI and ItchyQoL. Impact on pruritus and disease severity for subjects with CIU will be assessed via daily completion of UAS7 questionnaire. Schedules of these efficacy assessments are specified in Section 17.1.

- **WI-NRS score:** Subjects will be asked daily to assign a numerical score to the intensity of their most severe (worst) pruritus in the past 24 hours using a scale from 0 to 10, with 0 indicating no pruritus and 10 indicating the worst imaginable pruritus. The Worst-Itch NRS is provided in the Daily NRS Tool Section 17.2.

- The sleep quality NRS: Subjects will be asked daily to assign a numerical score to the quality of their sleep in the previous night using a scale from 0 to 10, with 0 indicating best possible sleep and 10 indicating worst possible sleep. The sleep quality NRS is provided in the Daily NRS Tool (Section 17.2).
- The difficulty falling asleep NRS: Subjects will be asked daily to assign a numerical score to the intensity of their difficulty falling asleep last night due to itch using a scale from 0 to 10, with 0 indicating not difficult at all and 10 indicating extremely difficult. The difficulty falling asleep NRS is provided in the Daily NRS Tool (Section 17.2).
- Pruritus VAS: Subjects will be asked to place a line perpendicular to the VAS line at the point that represents the intensity of their average pruritus experienced over the previous three days using a scale from 0 to 10, with 0 indicating no pruritus and 10 indicating the worst imaginable pruritus. Pruritus VAS scale is provided in Section 17.3.
- Sleep Loss VAS: Subjects will be asked to place a line perpendicular to the VAS line at the point that represents the intensity of their average sleeplessness experienced over the previous 3 nights using a scale from 0 to 10, with 0 indicating no sleeplessness and 10 indicating the worst imaginable sleeplessness at every visit. The scale of Sleep Loss VAS can be found in Section 17.3.
- The 5-D Pruritus Scale: This tool evaluates pruritus in five domains: duration, degree, direction, disability and distribution. Duration, degree and direction each consist of one item. The disability domain contains four items and the distribution domain includes 16 items. The first four domains are measured on a five-point Likert scale. The scores from each domain are added together to obtain a total 5-D score ranging from 5 (no pruritus) and 25 (most severe pruritus) (Elman 2010). The 5-D Pruritus Scale is administered every two (2) visits. The score of each of the 5 domains is obtained separately and summed together to get the total 5D-pruritus score.
 - For duration, degree and direction, use the number indicated below the response choice.
 - For disability, take the highest score for any of the 4 items (sleep, leisure/social, housework/errands, work/school).
 - For distribution, use the following scale:
 - 0-2 areas affected: score 1
 - 3-5 areas affected: score 2
 - 6-10 areas affected: score 3
 - 11-13 areas affected: score 4
 - 14 to 16 areas affected: score 5

5-D Pruritus Scale is specified in Section 17.4.

- DLQI: This tool is a 10-question questionnaire that considers symptoms and feelings, daily activities, leisure, school, personal relationships, and treatment. Each question,

except question 7, is answered on a scale of 0 to 3 (0 for not at all, 1 for a little, 2 for a lot, and 3 for very much), taking into account the previous week. For question 7: Subjects will be asked “Over the last week, has your skin prevented you from working or studying?” If answered yes, score=3; If no, a second question will be asked: “Over the last week how much has your skin been a problem at work or studying?” If further answered a lot, score=2; if a little, score=1; if not at all or not relevant, score=0. The DLQI total score is defined as the sum of all 10-question scores with minimum of 0 meaning no effect on quality of life and 30 meaning extremely large effect. DLQI questionnaire is provided in Section 17.5.

- ItchyQoL: This tool focuses on impact of pruritus on daily activities and on the level of psychological stress. It contains 22 items. The frequency items are scored using a 5-point Likert scale ranging from “never” to “all the time”. The bother items are scored from 1 (not bothered) to 5 (severely bothered). The recall period in ItchyQoL is the past week. The ItchyQoL total score is defined as the sum of all 22-items scores. The ItchyQoL symptom subscale score is calculated as the sum of question 1-6. The ItchyQoL functional subscale score is calculated as the sum of question 7-13. The ItchyQoL emotional subscale score is calculated as the sum of question 14-22. If there is only 1 item skipped in a subscale, the missing item value in the subscale will be imputed as the average of other non-missing item values. If 2 or more items are skipped in any given subscale, the subscale and total scores are set to missing. For other subscales that have less than 2 items skipped, those subscale scores need to be calculated. Total scores can be classified as little (0-30), mild (31-50), moderate (51-80), severe (81-110). ItchyQoL questionnaire is provided in Section 17.6 .
- The UAS7: Subjects will be asked daily to self-assess the number of wheals and the intensity of the subject’s pruritus. It is graded from 0 to 3 for each parameter and is averaged over seven consecutive days to obtain the UAS7 Score with a maximum score of 6. The greater the severity of the disease the higher the score. The total score will be calculated from weekly average of subcomponents. The UAS7 tool will be completed only by subjects in the CIU Cohort. UAS7 questions are can found in Section 17.7 .

Safety Assessments:

Safety will be assessed by monitoring of AEs, measurements of vital signs, physical examination, ECG evaluation, and clinical laboratory tests specified in Section 0. Assessments are specified in Section 17.1 .

PK Assessment:

PK blood samples will be collected according to Section 17.1.

[REDACTED]

[REDACTED]

[REDACTED]

[REDACTED]

3. DETERMINATION OF SAMPLE SIZE

This is a double-blind study. Each cohort will be independently analyzed. A total of approximately 26 subjects will be randomized in each cohort. The first 12 subjects will be randomized to the KPL-716 and the placebo arms in a 3:1 randomization ratio. The rest of the 14 subjects will be randomized in a 1:1 randomization ratio. There will be approximately 16 subjects and 10 subjects randomized to the KPL-716 arm and the placebo arm, respectively. Based on a two-sample t-test for the primary efficacy endpoint, change from baseline in weekly average of WI-NRS at Week 8, assumed mean changes of 4 for the KPL-716 arm and 1.5 for the placebo arm, a total sample size of 26 subjects per cohort will provide about 80% power to detect a 2.5-point mean difference with a standard deviation of 2.8, given a two-sided alpha of 0.2. Given the exploratory nature of this pilot study, the precision attained with the above cohort samples size is acceptable for early signal of efficacy assessments.

4. STUDY ANALYSIS SETS

4.1. Randomized Subjects

Randomized subjects will include all subjects whose date of randomization is not missing.

4.2. Modified Intent-to-Treat (mITT) Analysis Set

All randomized subjects who receive at least one (1) dose of KPL-716 or placebo and have at least one (1) post-baseline efficacy assessment in the double-blind Treatment Period will be included in the modified intent-to-treat (mITT) analysis set. All mITT analyses will be based on each subject's randomized treatment assignment.

4.3. Per Protocol (PP) Analysis Set

All mITT subjects who have no important protocol deviations that may potentially bias efficacy analyses of the study will be included in the PP set. Protocol deviations that may potentially bias statistical analyses will be defined in the SAP before database lock.

4.4. Safety Analysis Set

All randomized subjects who take at least one (1) dose of KPL-716 or placebo will be included in the Safety Analysis Set. Safety analyses will be based on the actual treatment (KPL-716 or Placebo) that was administered to each subject.

4.5. PK Analysis Set

Subjects who received KPL-716 and who had at least one (1) PK sample will be included in the PK population.

5. GENERAL ASPECTS FOR STATISTICAL ANALYSIS

5.1. General Methods

- All analyses and summaries will be produced using SAS® version 9.4 (or higher).

- Descriptive statistics in each cohort will be presented for all endpoints and will include number of subjects (n), mean, standard error (SE) and standard deviation (SD), first quartile (Q1), median, third quartile (Q3), minimum and maximum for continuous variables. Where specified, 80% and 95% Confidence Intervals (CI) of the mean will be calculated.
- For categorical variables (including binary variables), counts and percentages will be presented. Where specified, 95% 2-sided CI for proportions and 80% and 95% for odds ratios will be presented. CI for proportions will be calculated based on exact binomial distribution.
- For inferential statistical analyses in each cohort, the efficacy data will be analyzed and displayed by treatment group (KPL-716 and placebo) and visits. Unless otherwise specified, all tests will be two-tailed using pre-specified levels of significance.
- Subject listings in all randomized subjects, except the listing for screen failures will be provided for all efficacy and safety data. In general, the subject listings will be sorted by treatment group, subject number and assessment date (and time, if applicable).
- In general, 1 year will be defined as 365.25 days and 1 month will be defined as 30.4375 days (365.25 days/12 months).

5.2. Baseline Value and Change from Baseline

In general, baseline is defined as the last non-missing value obtained immediately prior to the first SC injection otherwise specified.

For daily collected efficacy endpoints (WI-NRS, difficulty falling asleep NRS, sleep quality NRS, UAS7), baseline is calculated as weekly average of non-missing scores from 7 days prior to Day 1, which is the day when the first SC injection is administered. For those daily collected efficacy endpoints, weekly average will be calculated based on every 7 days starting on the day after the start of injection (Day 1). Change and percent change from baseline in weekly averages will be summarized and compared between KPL-716 and placebo.

5.3. Study Day

Study day is defined as the number of days from the first date of treatment to the event/visit date.

It is calculated as follows:

If the event date falls on the date of treatment, or after the date of treatment,

$$\text{Study Day} = \text{Event or Visit Date} - 1^{\text{st}} \text{ Treatment Date} + 1$$

If the event date falls before the date of 1st treatment,

$$\text{Study Day} = \text{Event or Visit Date} - 1^{\text{st}} \text{ Treatment Date}$$

5.4. Analysis Visits

All data will be organized and analyzed according to the scheduled times as outlined in the protocol and by the visit denoted on the electronic case report form (eCRF), except for unscheduled and early termination (ET) visits. For unscheduled and early termination visits,

analysis visits will be assigned to closest visits based on event schedule table in Appendix 1. For multiple records on the same visit, CRF collected records will be used for the analysis. Summary by analysis visits will not include unscheduled analysis visits (after reassignment). However, unscheduled analysis visits will be included to define baseline, worst post baseline, or minimum, maximum post baseline and listings.

5.5. Time on study

Time on study will be defined as time from randomization date to the end of study. For ongoing subjects, cutoff dates will be used.

5.6. Missing Data Handling

No imputations will be performed for missing data for safety endpoints, unless otherwise specified. Missing data handling for efficacy endpoints is specified in Section 8 .

5.7. Multiple Comparisons/Multiplicity

No Multiplicity adjustment is planned.

6. STUDY SUBJECTS

6.1. Subject Disposition

The subject disposition will be summarized by treatment and overall based on safety population. All information will be presented in numbers and percentages in a summary table. The following information will be presented in subject disposition table:

- Screened subjects
- Randomized subjects
- Safety analysis set
- mITT analysis set
 - Subjects who completed treatment and the primary reasons for treatment discontinuation
 - Subjects who complete study and the primary reasons for study discontinuation

6.2. Protocol Deviations

A protocol deviation can be defined as any deviation from the study protocol that does not materially affect the safety of the subjects and/or the conduct of the study and/or its evaluation.

Important protocol deviations will be based upon the eCRF database and determined for all subjects by either medical review processes or programming based on the inclusion/exclusion criteria or other criteria presented in the protocol.

Current ICH GCP guidelines list the important protocol deviations that must be listed in the clinical report. Important protocol deviations are a subset of protocol deviations that may significantly impact the completeness, accuracy, and/or reliability of key study data or that may significantly affect a subject's rights, safety, or well-being. These may include:

- Subjects that are dosed on the study despite not satisfying the inclusion criteria;
- Subjects that develop withdrawal criteria whilst on the study but are not withdrawn;
- Subjects that receive the wrong treatment or an incorrect dose;
- Subjects that receive an excluded concomitant medication.

A summary table will be provided as the number (%) of subjects with at least one important protocol deviation and the number (%) of subjects in each category.

7. DEMOGRAPHICS AND BASELINE CHARACTERISTICS

The demographics and baseline characteristics data will be summarized in mITT and safety populations. Descriptive statistics will be provided for continual variables. Numbers and percentages of subjects will be tabulated for categorical variables.

7.1. Demographics

The following demographic variables will be summarized.

Age (years), calculated as the number of years between the date of birth and the date of signing the Informed Consent form.

- Age (years)
- Sex (Male or Female)
- Race (White, Black or African American, Asian, American Indian or Alaska Native, Native Hawaiian or Other Pacific Islander, Other)
- Ethnicity (Hispanic or Latino, Not Hispanic or Latino)
- Height (cm)
- Weight (kg)
- BMI (kg/m^2) = $\text{Weight}(\text{kg})/[\text{Height}(\text{m})^2]$

7.2. Screening and Baseline Disease Characteristics

The following screening and baseline characteristics will be summarized.

- Years since diagnosis (calculated relative to randomization date)
- Screening visits and baseline efficacy endpoints

7.3. Medical History

The medical history is coded using Medical Dictionary for Regulatory Activities (MedDRA version 21.1). The summary of medical history will be presented with number (%) by System Organ Class (SOC) and Preferred Term (PT). Each subject will be counted only once for each preferred term within a SOC per cohort. Similarly, for determination of MedDRA SOC incidences, subjects who experience multiple medical conditions under the same SOC will be counted only once for that SOC.

7.4. Prior and Concomitant Medications

All medications will be coded using the World Health Organization (WHO) drug dictionary. The WHO drug dictionary version B3 September 2018.

Prior medications are defined as medications that started before the first dose of study drug. Concomitant medications are defined as medications that (1) started before the first dose of study drug and continued into the treatment period, or (2) started on or after the date of the first dose of study drug. The number (%) of subjects who took prior and concomitant medications will be summarized on the anatomical class (ATC level 3) and preferred term (PT) by treatment and overall subjects.

For analysis purpose, topical corticosteroids [TCS], oral antihistamines [OH], and/or systemic corticosteroids which were used to treat pruritus or study skin conditions on or after first dose date, are defined as rescue medications. Transient use of TCS and systemic corticosteroids for non-study indications, are not considered as rescue medications. For example, transient use of TCS for injection site reactions, transient intranasal, or inhaled systemic corticosteroids for non-study indications are not considered as rescue medications. Identification of rescue medications will be based on medical review. Number and percentage of subjects who used rescue medication will be summarized. Time to 1st use of any rescue medication, such as time to 1st use of TCS, or time to 1st use of oral antihistamine will be summarized descriptively as well.

Prior TCS use regardless of indications, systemic corticosteroid, OH will be summarized as well, of which identification will be based on medical review.

Prohibited medications include, but not limited to, Systemic corticosteroids (IV/IM/oral) , Intralesional corticosteroids and intra-articular corticosteroids, Topical treatments including but not limited to corticosteroids, calcineurin inhibitors, phosphodiesterase inhibitors, retinoids, calcipotriol, capsaicin, camphor, polidocanol or tars, Antihistamines, Immunomodulators (for example, cyclosporine, methotrexate, retinoids, azathioprine, mycophenolate, and thalidomide) , Neuroactive drugs such as gabapentin and pregabalin, Cannabinoids, Opioid antagonists or agonists, Janus Kinase (JAK) inhibitors, Dupilumab and ustekinumab, Any other marketed biologic, Any investigational biologic drug, Any investigational non-biologic drug, Phototherapy involving UVA, UVB, or excimer, Tanning salon use which are used after first dose date. Topical corticosteroids and antihistamines may be provided in consultation with the Sponsor as rescue medications for an exacerbation of symptoms that is significant enough to warrant intervention. Subjects with CIU (Cohort 1) may use H1 antihistamine at approved and stable doses. For further details refer to the Pharmacy Manual. Identification of prohibited medications will be based on medical review. Number and percentage of subjects who used prohibited medications will be summarized as well if any data available.

7.5. Prior and concomitant procedures

The procedures are coded using Medical Dictionary for Regulatory Activities (MedDRA version 21.1). The prior and concomitant procedures are defined similarly as the prior and concomitant medications. The summary of prior and concomitant procedures will be presented with number (%) by System Organ Class (SOC) and Preferred Term (PT). Each subject will be counted only once for each preferred term within a SOC per cohort. Similarly, for determination of MedDRA SOC incidences, subjects who experience multiple procedures under the same SOC will be counted only once for that SOC.

8. EFFICACY ANALYSES

All efficacy analyses will be performed in the mITT analysis set. The analysis of primary efficacy endpoint will be repeated in the PP population. Analysis based on the mITT set will be the primary analysis and the analyses based on other analysis sets will be considered as the supportive analyses.

Line plots of LS Mean (SE) in percent change from baseline based on ANCOVA overtime will be presented and bar charts for responder analysis will be provided as well if needed for selected endpoints.

8.1. Analysis of primary efficacy endpoint

To minimize confounding impact on efficacy endpoints by rescue medications, efficacy assessments will be set to missing if collected in intervals:

- Systemic corticosteroids: from first date and afterward.
- TCS except for indication of injection site reactions from start date to end date plus 2 days if duration is ≤ 2 days, plus 7 days if duration is ≥ 3 days.
- Oral antihistamine, from start date to end date plus 1 day.

Then, all missing post baseline values including those due to early discontinuation are imputed with last observation carried forward (LOCF) method up to the end of the period with last non-missing CRF collected data or cutoff date whichever is first. Then weekly average will be calculated and Analysis of Covariance (ANCOVA) model will be fitted with treatment as factor and corresponding baseline value as covariate. Least square (LS) mean and standard error (SE) with 80% and 95% confidence intervals (CI), and p-value for difference of the between-treatment comparison of treatment with placebo will be provided. LS means (SE) and 80% and 95% CIs will be reported for each treatment as well.

As sensitivity analysis of primary endpoint, observed data will be used for ANCOVA model as well. If 50% or more data are missing for weekly average calculation at post baseline, the week will be set to missing.

In addition, randomization ratio and sex may be considered for exploratory purpose.

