### 5.3 Randomization

All subjects who are eligible for study participation will be randomized prior to study drug administration. Eligible subjects will be randomized to receive KPL-716 or placebo (Figure 2). The first 12 subjects of each cohort will be randomized to the KPL-716 and placebo arms in a 3:1 randomization ratio. The rest of the 14 subjects will be randomized in a 1:1 ratio. The randomization will be based on a computer-generated treatment randomization schedule prepared before the study by the Sponsor or designee.

An Interactive Web Response System (IWRS) will issue a unique treatment code to each subject, which will assign the treatment for the subject. Prior to each dosing, medical ID number of the vial to be administered will be obtained from (IWRS) based on the computer-generated treatment randomization schedule. The study drug will be prepared and administered according to instructions in the Pharmacy Manual.

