### **8.6.1 Primary Efficacy Endpoint Analyses**

The primary efficacy endpoint, the change from baseline in weekly average WI-NRS score at Week 8, will be analyzed using ANCOVA. The model will include treatment as the independent variable and baseline WI-NRS as the covariate. In addition, randomization ratio, and gender might be considered as covariates. Details for the modeling will be specified in the SAP.

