1. INTRODUCTION

The purpose of this Statistical Analysis Plan (SAP) is to describe statistical analysis methods and data reporting specifications for the preparation of the Clinical Study Report (CSR) and the programming outputs in the study.

The SAP is based on the protocol KPL-716-C202 dated 28 January 2019.

Per FDA request, the impact of COVID-19 on protocol deviations, efficacy and safety data should be documented in the statistical analysis plan. At the time of the finalization of this SAP, the overall sponsor assessment of the impact of COVID-19 to the integrity of efficacy and safety results appears to be limited and doesn't warrant specific mitigation measures in the SAP. More specifically:

All patients have completed week 7 visit dosing. This is the last dosing planned in the study. No doses were missed due to COVID-19. The primary efficacy endpoint of this study protocol is weekly average of worst itch NRS (WI-NRS) at week 8. This score can be entered by patients online, while at home, and therefore unlikely to be affected by COVID-19 restrictions on travel to clinical sites. In addition, other questionnaires which per protocol were filled out on-site, now are released to patients online and filled out at home. Taken together, the impact of COVID-19 restrictions on efficacy data (specifically LOCF analysis) is limited and there are no changes to the statistical analysis plan. Due to travel restrictions, some assessment such as physical evaluation etc. when done virtually may limit the ability to detect potential safety risks, however, apparent safety risks are not likely to be missed. The impact on safety remains to be clarified after final database lock, but not likely to affect the overall benefit-risk evaluation. Protocol deviations due to COVID-19 will be summarized in an additional category.

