17.9. Statistical Methods and SAS Codes

- **Analysis of Covariance (ANCOVA)**

The primary and secondary endpoints of change and percent change from baseline value by week will be analyzed using ANCOVA. The ANCOVA model includes factors of treatment, sex, and baseline value as a covariate. The following is an example of the SAS codes used to perform the analysis.

```
*****
```

* SAS Codes: *ANCOVA model*

* Variables in the model:

* chg = change from baseline in

* trt = treatment group code

* base = baseline value

* week = visit

```
*****;
```

```
proc mixed data=eff;  
  by week;  
  class trt;  
  model chg = trt base;  
  lsmeans trt /pdiff cl;  
run;
```

- **Fisher's Exact Test**

```
*****
```

* SAS Codes: Fisher's Exact Test

* Variables in the model:

* resp = response variable (Y/N or 1/0)

* trt = treatment group code

* week = visit number

```
*****;
```

```
proc freq data=dset order=data;  
  by week;
```

```
table trt*resp / alpha=0.05;  
exact relrisk fisher;  
output out=outname exact;  
run;
```

[REDACTED]

[REDACTED]

[REDACTED]

[REDACTED]

[REDACTED]

Signature Page for RIM-CLIN-001234 v1.0

Approval	[name] Legal 01-Oct-2021 12:48:07 GMT+0000
----------	---

Signature Page for RIM-CLIN-001234 v1.0

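### In cohorts that enrol past 12 subjects, the primary ANCOVA leaves out the 3:1-then-1:1 randomization stage, so about a quarter (at 18 to 26 subjects) of any between-stage difference not explained by baseline enters the treatment effect

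*SAP*

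**What the plan says.** Protocol 5.3 and SAP 2.3 set a two-stage allocation within each cohort: 12 subjects at 3:1, and then "The rest of the 14 subjects will be randomized in a 1:1 ratio". SAP 3 expects about 16 subjects on KPL-716 and 10 on placebo. The total is a ceiling in SAP 2.3: "Each cohort will enroll up to 26 subjects and contain three periods".

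For the primary endpoint, SAP 8.1 states: "Analysis of Covariance (ANCOVA) model will be fitted with treatment as factor and corresponding baseline value as covariate". The example code in SAP 17.9 agrees: "model chg = trt base".

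The allocation ratio is mentioned twice, each time as an option. Protocol 8.6.1 says "In addition, randomization ratio, and gender might be considered as covariates" and leaves the modelling details to the SAP. SAP 8.1 then says "In addition, randomization ratio and sex may be considered for exploratory purpose". The committed alternatives for the primary endpoint are an observed-data ANCOVA (SAP 8.1) and a per-protocol repeat (SAP 8), and neither adds stage.

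The model is also described inconsistently. The text of SAP 17.9 says "The ANCOVA model includes factors of treatment, sex, and baseline value as a covariate", while the code beneath it and SAP 8.1 leave sex out of the primary model.

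**The concern.** Randomization protects the comparison within each stage. When two stages with different ratios are pooled without a stage term, arm becomes correlated with enrolment order by design, not by chance. If early and late enrollees respond differently, for example because sites or case mix change, part of that difference is read as treatment effect. Baseline WI-NRS removes only the part that acts through baseline severity.

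Each cohort is a small screen of whether one disease responds, with a two-sided alpha of 0.2 and about 10 placebo subjects. The chance of a false favourable signal and the power of the test drive that decision. The bias can go either way, and the planned model cannot show which. Because the wording is optional, the choice of model also stays open until results are known.

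**Working it through.** **Inputs from the documents.** Stage 1: 12 subjects at 3:1, so 9 KPL-716 and 3 placebo. Stage 2: 14 at 1:1, so 7 and 7. Totals are 16 and 10. Difference 2.5 points, SD 2.8, two-sided alpha 0.2, two-sample t-test (SAP 3).

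**Input not in the documents.** D is stage 1 minus stage 2 mean improvement in WI-NRS, after allowing for baseline. It is an assumption, shown at 0.5, 1 and 2 points in either direction.

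**1. The plan's own figure.** The variance factor is 1/16 + 1/10 = 0.1625, so SE = 2.8 x sqrt(0.1625) = 1.129. The noncentral t with 24 df gives power 81.5%. The stated figure of about 80% is reproduced.

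**2. The leak.** Bias = D x (share of the KPL-716 arm from stage 1 minus share of the placebo arm from stage 1) = D x (9/16 - 3/10) = D x (0.5625 - 0.3000) = 0.2625 D. For D = 0.5, 1 and 2 this is 0.13, 0.26 and 0.53 points, or 5%, 10.5% and 21% of the 2.5-point target.

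**3. Dependence on cohort size.** With n = 12 + m and stage 2 split evenly, the leak is 9/(9 + m/2) - 3/(3 + m/2):

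| n | 12 | 14 | 16 | 18 | 20 | 22 | 24 | 26 |
|---|---|---|---|---|---|---|---|---|
| Leak | 0 | 0.150 | 0.218 | 0.250 | 0.264 | 0.268 | 0.267 | 0.2625 |

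**4. Operating characteristics at n = 26.** Simulation, 400,000 trials per setting, 9:3 then 7:7, within-stage SD 2.8, residual SD re-estimated in each trial, no baseline term. Error rates assume no treatment effect and D in the drug's favour. Power assumes a true difference of 2.5 and D against the drug.

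| Size of D | Favourable-tail error, no stage | Two-sided error, no stage | Power, no stage |
|---|---|---|---|
| 0 | 10% | 20% | 81.5% |
| 0.5 | 12.1% | 20.2% | 78.1% |
| 1 | 14.2% | 20.4% | 74.2% |
| 2 | 18.3% | 21.7% | 64.2% |

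With stage in the model, at every D, the favourable tail is 10.0 to 10.1%, two-sided error 19.9 to 20.1% and power 79.4 to 79.6%.

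**5. Check with a random baseline covariate** (100,000 trials). Without stage, the favourable tail is 14.1% and 18.1% at D = 1 and 2. Power is 80.4% with no drift and 72.7% and 62.7% at D = -1 and -2. With stage, power is about 78%. In a separate run where the stages differed only through baseline, the bias was about zero (0.009).

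**6. Cost of the stage term.** The effective sample size is 16 x 10/26 = 6.154 without stage and 9 x 3/12 + 7 x 7/14 = 2.25 + 3.50 = 5.75 with it. The variance ratio is 6.154/5.75 = 1.07, and the SE rises from 1.129 to 1.168. Power with treatment, baseline and stage (22 df) is 79.4%, ignoring chance baseline imbalance.

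**The case against.** **The harm is conditional.** The documents give neither a size nor a sign for D. Both stages share the same eligibility criteria, regimen and washout, and D = 2 would be 80% of the target effect. This stands: the leak fraction is certain, but drift is not.

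**The planned model can be the more accurate estimator.** Without stage the variance is 7.84 x 0.1625 = 1.274; with stage it is 7.84/5.75 = 1.363. Squared bias is 0.0689 x D^2, so the mean squared errors are equal at |D| = sqrt(0.0895/0.0689) = 1.14 points. Below that, leaving stage out has the smaller mean squared error. This also stands, but it is an argument about estimation. The stage model keeps its error rate and power whatever D is, for about 2 points of power.

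**The main test is two-sided, and its error barely moves.** True. A signal-seeking pilot, however, acts on the favourable tail, and the loss of power under an adverse shift is not small. A favourable shift would raise power, but only through bias.

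**It may not apply.** Cohorts enrol up to 26, and neither document shows that any went past 12. That limits the scope, and enrolment counts settle it.

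**The plan already names the factor, so a stage-adjusted sensitivity analysis would be enough.** It would close part of the gap, but the primary result would remain the one exposed to drift. The cost of reversing the two roles is low.

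**Conclusion.** The concern holds and should be fixed. At 26 subjects, 0.26 of any between-stage difference not explained by baseline WI-NRS passes into the primary estimate. The fraction is 0.25 to 0.27 from 18 to 26 subjects, 0.15 to 0.22 at 14 to 16, and zero at 12 or fewer. These fractions assume exact 9:3 allocation and an even stage 2 split.

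The consequence is modest and depends on D, for which the documents give no figure. At D = 1 the bias is 0.26 points against an SE of about 1.13, and its direction cannot be known in advance. The leak follows from the design itself, and no committed analysis removes it. The conflicting statements about sex in SAP 17.9 are a separate documentation error that the same edit can settle.

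**What to change.** - For every cohort that enrolled in both stages, make randomization stage (3:1 or 1:1) a fixed factor in the primary and continuous secondary ANCOVAs: `class trt stage; model chg = trt stage base;`.
- Keep the model without stage as a committed sensitivity analysis.
- State one model in SAP 8.1, the text of 17.9 and the code of 17.9, with sex labelled exploratory in all three.
- List the affected cohorts from blinded enrolment counts. SAP 1 reports that "All patients have completed week 7 visit dosing", so the counts should be available without treatment codes.

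The cost is SAP wording, one code term, one degree of freedom and a variance factor of 1.07. If there is no drift, power goes from 81.5% to 79.4%, or from 80.4% to about 78% once chance baseline imbalance is allowed for. The change does not reach the Fisher responder tests in SAP 8.3, which remain unadjusted for stage and should be read with that in mind.
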